11.2. IAEs definition

IAEs include episodes of hypoxia (SpO2<92%), use of unplanned lung recruitment maneuvers (ventilation strategies aimed to restore aeration of the lungs); airway pressure reduction (ventilation strategies aimed to lower peak and plateau pressure), presence of expiratory flow limitation (expiratory flow higher than zero at end-expiration as suggested by visual analysis of the expiratory gas flow curve), use of vasoactive drugs (any given to correct hypotension), and new arrhythmias (atrial fibrillation, sustained ventricular tachycardia, supraventricular tachycardia, or ventricular fibrillation).

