The here proposed study, conducted in patients undergoing surgery, aims to 1) describe the incidence and types of postoperative pulmonary complications (PPCs), 2) describe patient demographics, baseline characteristics, and intraoperative ventilation management, 3) describe the occurrence of intraoperative adverse events (IAEs), and 4) their associations with PPCs, and 5) assess the practice of intraoperative mechanical ventilation.

Study design

This is an observational investigator–initiated, international, multicenter, prospective, cross–sectional study.

Local investigators will capture data in an electronic CRF (eCRF), including patient demographics and baseline characteristics, intraoperative ventilator settings and ventilation parameters, and outcomes.

Study population

Patients are eligible for participation if: 1) adult and 2) receiving intraoperative ventilation during general anesthesia for surgery. We will exclude patients receiving ventilation outside of an operating room as well as patients receiving intraoperative ventilation during extracorporeal life support.

Main study endpoints

The primary endpoint is to report the number of patients with PPCs occurring in the first 5 postoperative days. As secondary endpoint, the practice of mechanical ventilation in patients undergoing general anesthesia for surgery will be ascertained including key intraoperative ventilator characteristics and respiratory system mechanics. Other secondary endpoints will include: incidence and type of IAEs; postoperative complications other than PPCs in the first 5 postoperative days; impact of intraoperative hemodynamic management on the occurrence of

PPCs, intensive care unit (ICU) admission and length of stay, hospital length of stay, and hospital mortality on day 28.

Study duration

The overall duration of the study is 18 months, with 9 months allocated for enrollment and data collection, and 9 months dedicated to statistical analysis.

Participating hospitals have to prospectively collect data in a consecutive manner within a predefined period of 1 week (7 days). Also, participating hospitals can decide on which period they choose to collect data, but data collection must take place during a predetermined time window of 8 weeks, following the ethical committee/internal review board approval.

Nature and extent of the burden and risks associated with participation, benefit and group relatedness

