1. RATIONALE

1.1. Practice of intraoperative mechanical ventilation

Ventilation during surgery carries potential risks for patients receiving general anesthesia (1). Postoperative pulmonary complications (PPCs) have been described to occur in up to 4% of general surgical cases (2). Nevertheless, patients at an elevated risk for PPCs have reported significantly higher incidence rates (3-7). PPCs are intricately tied to heightened degrees of both morbidity and mortality, even when PPCs are mild (8). In general surgery population (4) and surgical patients undergoing minimally invasive procedures (9), it has been demonstrated that specific ventilator settings impact the onset of PPCs. Since these two studies (4,8), numerous randomized clinical trials focused on the intraoperative ventilation regulation have investigated the impact of ventilator settings on PPCs in patients undergoing major surgery (9-10), abdominal surgery (6,11-13), or thoracic surgery (14-15). In addition, several systematic reviews and meta-analysis have been performed and published (2,16-19). The findings from these studies and meta-analyses may have significantly influenced ventilator management in these patient groups. Concurrently, evolving surgical practices favor minimally invasive procedures over open surgery, particularly in abdominal surgeries where deep Trendelenburg positioning can substantially affect ventilatory characteristics (20). As experience and knowledge about intraoperative ventilation in these challenging scenarios proliferate within medical communities, this evolving understanding is even translating into updated guidelines (21-23).

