5.1.2. Secondary outcomes

Secondary endpoints include: 1) ascertaining the practice of mechanical ventilation in patients undergoing general anesthesia for surgery including key intraoperative ventilator characteristics and respiratory system mechanics; 2) describing the incidence and type of IAEs; 3) describing postoperative complications other than PPCs in the first 5 postoperative days or hospital discharge whichever comes first; 4) describing the impact of intraoperative hemodynamic management on the occurrence of PPCs; 5) reporting intensive care unit (ICU) admission and length of stay, hospital length of stay, and hospital mortality on day 28.

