Weaning phase: at beginning and at the end of weaning phase, the following variables will be acquired: ventilatory mode, Vt (ml), PEEP (cmH₂O), pressure support over PEEP (if any) (cmH₂O), inspiratory trigger regulations, FiO₂, respiratory rate (breaths/min), SpO₂ (%), EtCO₂(mmHg or kPa), mean, systolic, and diastolic arterial pressure (either invasive or non-invasive), mmHg, heart rate (beats per minute).

It will also be recorded if aspiration is performed prior to tube removal. The number and type of IAEs will be acquired throughout the whole duration of surgical and anesthesiologic procedures (see "11" for definitions).

Peri-operative variables: duration of anesthesia procedure, duration of surgical procedure, tube type and size, type of anesthesia, type of analgesia (total endovenous, antibiotic prophylaxis, details on neuromuscular function monitoring and about the use of reversal agents (if any), total intra-operative fluid and total transfusion of blood products, temperature and hemoglobin at end of surgery (if clinically available). The possible admission to post-anesthesia care unit (PACU) and the eventual administration of non-invasive respiratory support (NIRS), namely, high flow oxygen therapy, continuous positive airway pressure, and non-invasive bilevel positive airway pressure ventilation, and the settings will be recorded.

Post-operative variables: vital signs involving SpO₂, heart rate, systolic, diastolic, and mean arterial pressure, body temperature if assessed, eventual arrythmias occurrence, and the blood gas analysis parameters (optional assessment) will be hourly collected in the immediate post-operative period or PACU stay, and at the discharge to surgical ward or ICU.

Follow up (day 0 to 5): PPCs are recorded from the medical chart on day 0 (end of surgery to 23:59h) and on days 1,2,3,4 and 5 post-operative (each day runs from 00:00 AM to 23:59 PM). Follow–up is completed on the day of discharge or on day 5 if the patient is still admitted.

On day 0 the following variables are collected: IMV after discharge from the operation room, admission to ICU/PACU after surgery, PPCs (see "11").

On day 1,2,3,4 and 5 the following variables will be collected: any new admission to ICU; any new or prolonged IMV; PPCs (see "11").

The data mentioned above are considered essential to defined as "complete" each patient's medical record.

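### Section 11.2 counts airway pressure reduction as an intraoperative adverse event without an unplanned or corrective condition, so planned pressure-limiting ventilation can be scored as an event

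*Protocol*

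**What the plan says.** Section 11.2 of the Protocol defines IAEs in one sentence. Three of its items are things the anesthetist does rather than things that happen to the patient:

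- The first is "use of unplanned lung recruitment maneuvers", explained there by their purpose of reopening the lungs.
- The second, which is the item at issue, reads "airway pressure reduction (ventilation strategies aimed to lower peak and plateau pressure".
- The third is "use of vasoactive drugs (any given to correct hypotension".

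The first is limited by the word unplanned and the third by its purpose of correcting hypotension. The second carries neither kind of limit.

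On capture, section 5.2 says: "The number and type of IAEs will be acquired throughout the whole duration of surgical and anesthesiologic procedures". It points to section 11 for the definitions and lists no field that separates planned from unplanned actions. On use, section 5.1.2 makes IAEs a secondary endpoint ("describing the incidence and type of IAEs"), and the main objectives in the Summary are to "describe the occurrence of intraoperative adverse events (IAEs), and 4) their associations with PPCs". Secondary endpoint 1 in section 5.1.2 is the practice of mechanical ventilation itself.

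**The concern.** A ventilation plan set before induction to keep peak and plateau pressure low satisfies the item as worded, and the capture window covers the whole procedure. A site that follows the text literally would record an adverse event in a patient whose ventilation was uneventful. A site that reads the item as a reaction to a high pressure would not. The same behaviour can therefore be counted as ventilation practice under one secondary endpoint and as an adverse event under the next.

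Three things are at stake: the incidence of this item and of any pooled IAE variable, comparability between centers in a study that also plans a geo-economic comparison, and the association between IAEs and PPCs. The last suffers because patients without a true event are moved into the event group.

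The rule is applied by site staff at data entry, so an analysis plan can repair it only in part. The hourly settings show pressures but not intent. Each center collects for one week (section 3.2), and the link between record and patient is destroyed at the end of monitoring (section 8.1).

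**Working it through.** **The plan's own figure.** The Protocol's only design figure is a 95% Clopper-Pearson width of 0.0119 for a 10% PPC rate in 10,000 patients (section 4.4). With 1,000 events the exact limits are 0.09419 and 0.10605, a width of 0.01186, so it reproduces. This point does not depend on it.

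**Comparison of the text.** Section 11.1 draws the planned/unplanned line explicitly: supplementary oxygen must be unplanned and oxygen given as standard care is excluded, and postoperative invasive ventilation must be unplanned if new or prolonged. Section 11.2 draws a similar line for recruitment maneuvers and vasoactive drugs. Among the treatment-type items of section 11.2, airway pressure reduction alone has no such line.

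**Size for this item alone.** The documents give no inputs, so all of these are assumptions: true reactive reductions in 3% of patients with relative risk (RR) 2.0 for PPCs, and a planned pressure-limiting strategy in 50%, independent of those events, with RR t for PPCs. Let f be the share of planned strategies that sites score as an event. Risks are relative to a patient with neither.

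- Scored: mass = 0.03 + 0.485f; risk sum = 0.015×2 + 0.015×2t + 0.485·f·t
- Not scored: mass = 0.485(1−f) + 0.485; risk sum = 0.485(1−f)t + 0.485
- Apparent RR = (scored sum / scored mass) ÷ (unscored sum / unscored mass)

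| f | Item incidence | RR if t = 1.0 | RR if t = 0.8 |
|---|---|---|---|
| 0 | 3.0% | 2.00 | 2.00 |
| 0.1 | 7.9% | 1.38 | 1.31 |
| 0.2 | 12.7% | 1.24 | 1.14 |
| 0.4 | 22.4% | 1.13 | 1.01 |
| 0.5 | 27.3% | 1.11 | 0.98 |
| 1.0 | 51.5% | 1.06 | 0.86 |

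For f = 1 the arithmetic is 0.545/0.515 = 1.06 and 0.442/0.515 = 0.86. Other inputs matter too. With f = 1 and t = 0.8, planned use of 10% instead of 50% gives 0.1364/0.127 = 1.07, and a true event rate of 30% instead of 3% gives 0.82/0.65 = 1.26.

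**Size for a pooled IAE variable.** Again by assumption: any true IAE in 10% or 30% of patients, with RR 1.5 or 2.0; planned pressure limitation in 10%, 30% or 60% of the rest, with RR 1.0, 0.8 or 0.6; overall PPC rate 10%; every planned strategy scored. The baseline risk is p0 = 0.10 / (sum of group share × group RR). The IAE-PPC odds ratio (OR) is then computed with the planned group left out of, or put into, the IAE group.

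One case in full: 10% true IAEs, RR 1.5, 30% planned, no effect of planning.

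- p0 = 0.10/(0.15 + 0.27 + 0.63) = 0.0952, and the risk with a true IAE is 0.1429
- Planned use excluded: OR = (0.1429/0.8571)/(0.0952/0.9048) = 1.58
- Planned use included: risk = (0.10×0.1429 + 0.27×0.0952)/0.37 = 0.1081, OR = 1.15

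Over the 36 combinations:

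- The OR is 1.57 to 3.11 with planned use excluded and 0.72 to 1.94 with it included; it is lower with inclusion in every combination.
- Apparent incidence rises from 10% to 19–64%, or from 30% to 37–72%.
- The OR falls below 1 in 8 combinations. All of them have a protective planned strategy (RR 0.8 or 0.6) used in at least 30% of the remaining patients. In 4 of the 8 it lies between 0.97 and 0.99.
- With true IAEs at 30% and RR 2.0 it stays between 1.20 and 1.94.

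**The case against.** The literal reading can be called strained. The section defines events, and a reduction ordinarily means lowering a pressure that is already present. Section 5.2 acquires a count, which suits discrete occurrences better than a strategy in force throughout. Neighbouring items are occurrences or corrections. The one semicolon in the list may separate the recruitment item from this one, or may join the two under the word unplanned. All of this stands. It shows that the text is ambiguous, not that it settles on the reactive reading, and ambiguity is enough for sites to differ.

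There are also partial safeguards. Mode, tidal volume, PEEP and airway pressures are recorded at induction and hourly, so a constant strategy can often be told from a change during the case. Sites are trained on the eCRF (section 8.1) and work to standard operating procedures with consistency checks (section 8.2), and coding instructions may sit there. The secondary endpoint already covers the type of IAE, so reporting incidence by item is largely planned. These limit the harm, but none of them states what this item counts.

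A reader might infer that the association with PPCs will vanish or change sign, or that the signal of all true IAEs is lost. The documents support neither. They give no event rate and no frequency of planned pressure limitation. The rationale (section 1.1) says "it has been demonstrated that specific ventilator settings impact the onset of PPCs", which gives no direction of effect; the Summary speaks of prevention by certain settings but gives no size. In the first table, a clear reversal needs a protective strategy with well over half of the planned cases scored, and with t = 1.0 the RR never falls below 1. Hypoxia, recruitment, flow limitation, vasoactive drugs and arrhythmias are untouched when analysed by type.

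**Conclusion.** The point holds as a defect of definition. The item lacks the limit that its neighbours carry and can take in planned ventilation practice. The supported consequences are inconsistent scoring between sites, inflated incidence of this item and of any pooled IAE variable, and a weakened association with PPCs. The size cannot be derived from the documents; the ranges above are illustrations.

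The weakening rests on one further assumption: that patients with planned pressure limitation have a PPC risk no higher than the rest. If the strategy is chosen mainly for patients at higher risk, the label would carry that confounding instead, which is still not the effect of an adverse event.

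The reach is limited. The primary PPC endpoint and the sample size are unaffected. The IAE-PPC association is an objective in the Summary but appears neither among the objectives of section 2.2 nor among the endpoints of section 5.1.2. The item should still be corrected before sites collect data, because it cannot be fully recoded afterwards.

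**What to change.** 1. In section 11.2, reword the item as *unplanned airway pressure reduction*, meaning an unplanned change of ventilator settings during the case made in response to airway pressure. This makes it parallel to "use of unplanned lung recruitment maneuvers".
2. State in section 11.2 and in the eCRF help text that settings chosen as the planned strategy are recorded as ventilator settings and not as an IAE.
3. Analyse the IAE-PPC association by IAE type as well as pooled.

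This sets no pressure threshold and no clinical rule. What counts as a response to airway pressure remains the anesthetist's judgement, so some variation between sites will stay. The cost is one wording change, one line of help text and a lower reported IAE incidence.

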2.2. Study objectives

- To describe the incidence and type of PPCs in the first 5 postoperative days;
- To describe associations of patient, surgery, and intraoperative ventilation characteristics with the occurrence of PPCs;
- To describe the impact of intraoperative hemodynamic management on the occurrence of PPCs;
- To describe the occurrence of intraoperative adverse events (IAEs); and
- To describe geo
 economic differences in intraoperative ventilation management.

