5.2. Data collection

Hospitals participating in the study will proactively gather data from all surgical procedures involving patients in a consecutive manner, under the supervision of the local investigator. All data collected are integral to standard clinical care. A visual representation of the trial's design can be found in Figure 2.

Patient characteristics: information such as baseline characteristics and preoperative risk factors essential for identifying patients prone to PPCs. This includes details like age, gender, height, weight, predicted body weight, smoking status, comorbidities, preoperative biochemical exams, peripheral oxygen saturation (SpO2), frailty scale, and American Society of Anesthesiologists (ASA) score. Additionally, data on the type and indication for surgery will be gathered for computing the Assess Respiratory Risk in Surgical Patients in Catalonia (ARISCAT) and Revised Cardiac Risk Index (RCRI). Surgical characteristics: urgency degree of surgery (emergent vs urgent vs elective procedure), planned duration of surgery, type of surgical procedure, and surgical technique.

Operator characteristics: gender, years of anesthesiologist practice, and experience in critical care.

Center characteristics: academic vs non-academic, grade of workload.

Data collection on day 0: type of anesthesia (volatile anesthetic medications or intravenous agents); IMV settings and monitored parameters will be intra-operatively collected at induction and hourly including ventilatory mode, peak inspiratory pressure (cmH₂O), plateau pressure (cmH₂O) (if available), inspiratory to expiratory ratio (I/E), and plateau time (seconds or %), mean airway pressure (cmH₂O), actual inspired tidal volume (Vt) (ml), applied positive end-expiratory pressure (PEEP) and total PEEP with any intrinsic PEEP (cmH₂O) (if present), respiratory rate (breaths/min), dynamic and static respiratory system compliance (cmH₂O/ml) (if clinically available); airway

resistance (Raw) (cmH₂O/(l/sec)) (if clinically available), inspired oxygen fraction (FiO₂), use of recruitment maneuvers (number and type), peripheral oxygen saturation (SpO₂) (%), end-tidal carbon dioxide tension (EtCO₂) (mmHg or kPa), mean, systolic, and diastolic arterial pressure (either invasive or non-invasive) (mmHg), heart rate (beats per minute), body temperature (°C) (if assessed), and arterial blood gases analysis (if present).

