6. STATISTICAL ANALYSIS

The demographic and baseline characteristics of the study population will be reported. Continuous variables will be summarized using median and interquartile range (IQR), and categorical variables will be summarized using frequencies and percentages. The comparison among groups for categorical variables will be performed by considering the Chi-square test or Fisher's exact test whatever is appropriate; for continuous variables, the Wilcoxon -Rank Sum test will be used.

The primary endpoint, namely, the PPCs rate, will be calculated together with the 95% confidence interval (CI). Moreover, the impact of the patient's characteristics on the risk of PPCs will be handled by using appropriate statistical models, such as Logistic Regression. These analyses will be adjusted for potential confounders identified at the study's outset, providing insights into factors that may influence PPCs rates among the patients population subjected to surgery. The 95% CIs on the model OR (Odds Ratios) and predicted probability of PPCs, according to the patient's profile, will be estimated. Handling of missing data will be addressed through robust methods like multiple imputation or complete case analysis, depending on the nature and extent of the missingness. Sensitivity analyses will further assess the robustness of the findings, examining how different assumptions about the missing data and analytical methods influence the results.

The significance of differences will be defined by the p-values, with a value of less than 0.05 considered statistically significant.

The following planned secondary analyses will be performed:

- Cardiac vs non-cardiac surgery
- Elective vs non-elective procedures
- Obese vs non-obese patients
- Open vs minimally invasive/robotic surgery

- Comparison among the different obesity classes
- Practice of weaning from invasive mechanical ventilation
- Impact of geo-economical difference

The analyses will be performed by using R 3.4.2.

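### Endpoint 4 asks how intraoperative hemodynamic management relates to PPCs, but the Section 5.2 lists hold no vasoactive-drug item; such drugs are captured only as an adverse event, when given to correct hypotension

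*Protocol*

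**What the plan says.** Section 2.2 lists as an objective "To describe the impact of intraoperative hemodynamic management on the occurrence of PPCs". Section 5.1.2 repeats it as the fourth secondary endpoint: "describing the impact of intraoperative hemodynamic management on the occurrence of PPCs".

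The data for this are set out in Section 5.2:

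- At induction and hourly, the hemodynamic items are "mean, systolic, and diastolic arterial pressure (either invasive or non-invasive) (mmHg), heart rate (beats per minute), body temperature". Pressures and heart rate are taken again at the start and end of weaning.
- Among the peri-operative variables, the items that describe hemodynamic treatment are "total intra-operative fluid and total transfusion of blood products".
- For adverse events, "The number and type of IAEs will be acquired throughout the whole duration of surgical and anesthesiologic procedures".

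Vasoactive drugs are mentioned once in the protocol, in the Section 11.2 list of intraoperative adverse events (IAEs): "use of vasoactive drugs (any given to correct hypotension". Section 6 does not say which variable or variables make up the hemodynamic exposure.

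**The concern.** Blood pressure and heart rate are the result of management. Fluids, blood products and vasoactive drugs are the management itself. The first two are collected as treatment. The third enters the dataset only through an event definition that depends on why the drug was given. A patient supported by a planned infusion, or given an inotrope for a reason other than hypotension, meets no recording rule in the protocol and looks the same as a patient who received nothing.

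At stake is how far endpoint 4 can be answered. A statistical analysis plan can define an exposure from collected data but cannot supply data that were never collected. Later retrieval is also closed off: each center collects for one week (Section 3.2), and the link to the individual patient is destroyed at the end of monitoring (Section 8.1). Imputation does not help either, because unrecorded use is not flagged as missing; it reads as absence.

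**Working it through.** **1. What each list records**

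| Aspect of management | Recorded as treatment (5.2) | Recorded as IAE (11.2) |
|---|---|---|
| Fluids | yes, total | no |
| Blood products | yes, total | no |
| Vasoactive drug to correct hypotension | no | yes |
| Vasoactive drug, planned or preventive | no | no |
| Vasoactive drug for another reason | no | no |
| Recruitment maneuver, any | yes, number and type | no |
| Recruitment maneuver, unplanned | yes, number and type | yes |

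The last two rows are the useful comparison. For recruitment maneuvers the protocol records all use as management and singles out unplanned use as an event. For vasoactive drugs it has the event half only.

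**2. Whether another item fills the gap**

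The data-collection list in the Summary has no vasoactive item. The SOFA score is collected after ICU/PACU admission, on a form that centers may leave out for workload, so it does not describe the operation. No other section mentions these drugs.

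**3. The plan's own figure**

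The sample-size statement is not affected. The exact (Clopper-Pearson) 95% interval for 1,000 PPCs in 10,000 patients is 0.09419 to 0.10605, a width of 0.01186, which rounds to the stated 0.0119.

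**4. Illustration if the IAE flag were the exposure**

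Only the overall PPC rate of about 10% comes from the protocol (Section 4.4). Everything else is assumed:

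- E, the share of patients truly given a vasoactive drug: 20% to 60%;
- s, the share of those with planned or preventive use only, hence coded unexposed: 10% to 50%;
- true odds ratio (OR) 1.5 or 2.0, with equal PPC risk p1 in planned and corrective users, and p0 in patients given no drug.

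Risk in the group coded unexposed = (E·s·p1 + (1−E)·p0) / (E·s + 1−E).

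Example: E = 0.4, s = 0.3, OR = 2.0. An overall rate of 10% gives p0 = 0.0744 and p1 = 0.1384 (check: 0.4 × 0.1384 + 0.6 × 0.0744 = 0.100). The group coded unexposed has (0.12 × 0.1384 + 0.6 × 0.0744) / 0.72 = 0.0851. Observed OR = (0.1384/0.8616) / (0.0851/0.9149) = 1.73.

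| True OR | Observed, mildest case (E = 0.2, s = 0.1) | Observed, strongest case (E = 0.6, s = 0.5) |
|---|---|---|
| 1.5 | 1.48 | 1.24 |
| 2.0 | 1.96 | 1.42 |

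**5. Direction when planned users differ in risk**

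Keep E = 0.4, s = 0.3, p0 = 0.0744 and a corrective-user risk of 0.1384. Let planned users have PPC risk r (assumed). The overall rate then moves slightly from 10%.

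- r = 0.20: all users (0.28 × 0.1384 + 0.12 × 0.20) / 0.4 = 0.1569, so the OR for any use is 2.31. Coded unexposed (0.12 × 0.20 + 0.6 × 0.0744) / 0.72 = 0.0953, so the observed OR is 1.52.
- r = 0.05: all users (0.28 × 0.1384 + 0.12 × 0.05) / 0.4 = 0.1119, so the OR for any use is 1.57. Coded unexposed (0.12 × 0.05 + 0.6 × 0.0744) / 0.72 = 0.0703, so the observed OR is 2.12.

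The bias is downward in the first case and upward in the second.

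**The case against.** The strongest reply is that no section makes the IAE flag the exposure for endpoint 4. Defining the exposure is commonly left to the analysis plan, which is not at hand. If the exposure is built from pressures, fluids and transfusion, nobody is misclassified; a component is simply absent. This stands, and it is why misclassification is stated here as one of two possibilities.

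Three stronger readings are tempting, and the documents do not support them:

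- *That endpoint 4 cannot be answered at all.* Serial pressures and heart rate, total fluid, transfusion, corrective vasoactive use and new arrhythmias are all collected, and the objective is worded as descriptive. Part of the endpoint is supported.
- *That drug and hypotension cannot be separated.* The flag by itself merges them, but hypotension can be derived from the recorded pressures, within the limits of hourly sampling. Hypotension that is untreated, or treated with fluid alone, is therefore not lost for being outside the IAE list.
- *That the comparison "Cardiac vs non-cardiac surgery" suffers most.* Section 6 lists it as a separate secondary analysis, not tied to endpoint 4. PPC incidence in the two groups needs no vasoactive field. How often planned support is used, and in whom, is not stated anywhere.

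It can also be said that the hourly list is introduced as non-exhaustive, that the peri-operative list contains an unclosed bracket, and that the eCRF is not shown. A field may exist. If so, the protocol should list it, because Section 5.2 is where it says what makes a record complete.

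**Conclusion.** The gap is real and limited. As written, the protocol captures vasoactive drugs only as an IAE tied to hypotension, so planned, preventive or other use is indistinguishable from no use. Endpoint 4 then either lacks a vasoactive component or, if the flag is used as the exposure, misclassifies these patients. The size and direction of any resulting bias are unknown. The odds ratios above rest on assumed inputs and show only that the effect could range from negligible to material. One secondary endpoint and the matching objective are affected; the primary PPC rate and its precision are not. Confidence is high on what the protocol lists and lower on what the eCRF may hold.

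**What to change.** Add one item with two parts to the peri-operative variables in Section 5.2: any intraoperative vasopressor or inotrope use (yes/no) and, if yes, whether it was planned/preventive or given to correct hypotension. State that the endpoint 4 exposure is built from this item together with fluids, transfusion and the recorded pressures. Keep the Section 11.2 event as a separate outcome, as the protocol already does for recruitment maneuvers. If the eCRF already holds such a field, listing it in Section 5.2 is enough.

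The cost is slightly more data entry per patient and a short edit to Section 5.2, plus a line stating the exposure. It changes nothing in patient care. The item has to be in place before a center starts its collection week, because it cannot be reconstructed once the patient link is destroyed.
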